4.7 REPLACEMENT OF SUBJECTS

Enough subjects will be enrolled in the trial to ensure that approximately 105 subjects are randomized into the T+M Period. Randomized subjects will not be replaced.

4.8 ELIGIBILITY FOR EXTENSION STUDY

Subjects who complete the 12-week Maintenance Period of this study will be eligible to enroll in a planned, separate, open-label extension trial of ZX008 if they meet Inclusion/Exclusion criteria for that study regarding their suitability for continued participation in a trial of fenfluramine.

Subjects must complete the entire 12-week Maintenance Period in order to be offered enrollment into the separate, open-label extension trial of ZX008. Those subjects who do not complete the 12-week Maintenance Period of the study may, on a case-by-case basis, be eligible for entrance into the separate open-label extension study after consideration of the circumstances of the early termination and the potential benefit-risk of continued participation in a ZX008 trial. The decision whether to permit open-label extension study participation resides solely with the sponsor, who may consult with the site investigator, the IPCAB and/or the IDSMC.

5. INVESTIGATIONAL MEDICINAL PRODUCT INFORMATION

Confidential Page 42 of 182

ZX008/matching placebo will be administered in the current study. A brief description of the ZX008 product is provided below (Table 2).

Table 2: Investigational Medicinal Product – ZX008

	Study Product
Substance Code	ZX008
Active Substance (INN)	Fenfluramine Hydrochloride
Trade Name	Not applicable
Formulation (including dosage form and strength)	Solution 1.25, 2.5, and 5 mg/mL
Route/Mode of Administration	Oral
Manufacturer	PCI Pharma Services on behalf of Zogenix
	International Limited

5.1 IDENTITY OF INVESTIGATIONAL MEDICINAL PRODUCT

ZX008 drug product is an oral aqueous solution of fenfluramine hydrochloride buffered to pH 5 and provided in concentrations of 1.25 mg/mL, 2.5 mg/mL, and 5 mg/mL. The excipients selected have been approved for use in the formulations of currently marketed drug products and are considered to be safe. The solution formulations will be suitably flavored and colored, and will contain preservatives and a thickening agent. The product is sugar free and is intended to be compatible with a KD.

The formulation will be provided in bottles with tamper-evident, child-resistant caps. The clinical trials material will be supplied in 1 bottle size with nominal fill volume of 120 mL. Matching placebo also will be provided. Doses to be studied include 0.2 mg/kg/day and

0.8 mg/kg/day divided into two daily (BID) doses, up to a maximum of 30 mg/day. An intermediate dose of 0.4 mg/kg/day will be used for titration. The concentration of ZX008 oral solution received by subjects (1.25 mg/mL, 2.5 mg/mL, and/or 5 mg/mL) will be randomized across the 3 available concentrations in order to ensure blinding.

If the parent/caregiver is unable to administer the full dose due to spillage (e.g., dose was spilled during measuring, subject spit dose out during administration), he/she should attempt to give the full dose noting the extra amount used to fulfill the dose. **Care must be taken not to overdose.** If the amount spilled is not known, the parent/caregiver should not give additional medication to avoid potential overdose.

5.1.1 Labeling and Packaging

The ZX008 product will be packaged and labeled according to current International Conference on Harmonization (ICH), Good Manufacturing Practices (GMP), and Good Clinical Practices (GCP) guidelines, and national legal requirements.

Dosing directions for the product can be found in the IMP handling instructions for the study subjects and for the investigator.

Confidential Page 43 of 182

5.2 DESCRIPTION OF REFERENCE TREATMENT, COMPARATOR, AND/OR PLACEBO

Placebo solution is identical in aspect and composition to ZX008 and is composed of identical ingredients used in the ZX008 formulation, except that it does not contain the active ingredient, fenfluramine hydrochloride.

No comparators or reference treatments will be used.

5.2.1 Labeling and Packaging

Placebo solution will be packaged in an identical manner to ZX008. The matching placebo product will be packaged and labeled according to current ICH, GMP, and GCP guidelines, and national legal requirements.

Dosing directions for the product can be found in the IMP handling instructions for the study subjects and for the investigator.

5.3 SHIPMENT AND STORAGE

IMP will be supplied to the study sites by the sponsor or its delegate.

All IMP will be transported, received, stored, and handled strictly in accordance with the container or product label, the instructions supplied to the research site and its designated pharmacy, the site's standard operating procedures, and applicable regulations. IMP must be stored separately from normal hospital or practice inventories, in a locked facility with access limited to the investigator and authorized personnel. The investigator must ensure that the IMP is dispensed only to subjects enrolled in this study according to this study protocol.

Appropriate storage temperature and transportation conditions will be maintained for the study drug from the point of manufacture up to delivery of the study drug. Study medication must be stored at 15-25°C (59-77°F) with excursions of 5-30°C (41-86°F) permitted; do not freeze.

Storage and handling instructions of the IMP maintained at the subject's home are described in the subject's IMP handling instructions.

All unused IMP will be saved by the site for final disposition according to the sponsor's directive.

5.4 IMP ACCOUNTABILITY

The investigator or delegate will confirm receipt of all shipments of the IMP in writing using the receipt form(s) provided by the sponsor or vendor.

Assignment of ZX008 or placebo to the subject will be handled through an interactive voice randomization (IVR) or Interactive Web Response (IWR) platform. The investigator or delegate will be required to register the subject through IVR/IWR and all study medication will be assigned to the subject through the IVR/IWR. The IVR/IWR will also maintain a log of all received and

Confidential Page 44 of 182

dispensed medication.

All supplies must be accounted for throughout the study using the drug accountability form provided by the sponsor before the start of the study. At the end of the study, the dated and signed (by the investigator or delegate, e.g., pharmacist) original drug accountability form must be retained at the study site as verification of final drug accountability.

Records for the delivery of the IMP to the study site, the inventory at the study site, the use by each subject (use by subject will be documented in the subject diary), and the destruction or return of the IMP to the sponsor must be maintained by the investigator (or delegate). The records will include dates, quantities, batch numbers, and unique code numbers assigned to the IMP and to the subjects. The investigator must maintain records documenting that subjects were provided with the doses of the IMP specified in this study protocol. Furthermore, the investigator must reconcile all IMPs received from the sponsor. The investigator must provide reasons for any discrepancies in drug accountability. Forms will be provided by the sponsor to ensure standardized and complete drug accountability.

5.5 TREATMENT ADMINISTRATION

5.5.1 Randomization

Upon completion of the Baseline Period, subjects who qualify for the study will be randomized (1:1:1) in a double-blind manner to receive 1 of 2 doses of ZX008 (0.2 mg/kg/day, 0.8 mg/kg/day; 30mg/day maximum) or placebo. The randomization will be stratified by age (<6 years, ≥6 years) to ensure balance across treatment arms, and at least 40% of subjects will be in each age group. Subjects will be assigned a randomization number by the IVR/IWR system upon confirmation that subject qualifies for enrollment in the Titration Period. Once a randomization number is assigned to a subject, the site will record the subject's initials and identification number on the corresponding study drug bottles. Each bottle will contain the assigned treatment (ZX008 0.2 mg/kg/day, ZX008 0.8 mg/kg/day, or placebo). ZX008 and placebo will be identical, thus rendering the study drug and placebo indistinguishable. For each IMP bottle and randomization number assigned, the following information will be recorded on the drug accountability form: subject initials, unique bottle number, date each bottle is assigned, and drug used and unused during the study.

5.5.2 Titration Period

The investigator (or delegate) will dispense IMP only to subjects included in this study following the procedures set out in this study protocol.

Study medication will be administered as equal doses BID in the morning and in the evening approximately 12 hours apart, with food. Each dose should be separated by a minimum of 8 hours and a maximum of 12 hours. A missed dose of study medication may be taken later up to 8 hours before the next scheduled dose; otherwise, the missed dose should not be given.

Administration of the IMP will be based on the randomized dose and subject's weight (kg) at

Confidential Page 45 of 182

Visit 3 (Study Day -1). At Visit 8 (Study Day 43), if the subject's weight (kg) has changed ±25% of the weight at Study Day-1, the IMP dose will be recalculated. Subjects should be dosed using the oral dosing syringe provided.

In order to maintain the blind across all dose groups (Section 5.6) and allow step titration to the high dose, the dose for each subject will be titrated starting with a dose of ZX008

0.2 mg/kg/day (or placebo equivalent) BID. After 4 days at this dose level (Study Day 5), subjects randomized to the ZX008 0.8 mg/kg/day group will increase their dose to 0.4 mg/kg/day (maximum 30 mg/day) while doses in the other two groups will remain constant. On Study Day 9, the dose for the 0.8 mg/kg/day group will increase to the target dose or a maximum of 30 mg/day. The titration is expected to take a total of 14 days (Table 3). A new bottle of IMP will be started by the subject at each level of the titration step. See Section 5.6 for more information about the volume of ZX008 or placebo to be administered.

Table 3: Titration Algorithm

	Titration Step 1	Titration Step 2	Titration Step 3		
Randomized Group	Study Day 1-4	Study Days 5-8	Study Days 9-14		
ZX008 0.2 mg/kg/day	ZX008 0.2 mg/kg/day	ZX008 0.2 mg/kg/day	ZX008 0.2 mg/kg/day		
ZX008 0.8 mg/kg/day	ZX008 0.2 mg/kg/day	ZX008 0.4 mg/kg/day	ZX008 0.8 mg/kg/day		
Placebo Placebo Placebo Placebo					
Note: maximum daily dose of ZX008 is 30 mg					

5.5.3 Maintenance Period

After completion of the Titration Period, subjects will enter the Maintenance Period and continue to receive the randomized dose of ZX008 or placebo and be treated for an additional 12 weeks. Study medication will continue to be administered BID in the morning and in the evening, approximately 12 hours apart, with food. Each dose should be separated by a minimum of 8 hours and a maximum of 12 hours. A missed dose of study medication may be taken later up to 8 hours before the next scheduled dose; otherwise, the missed dose should not be given.

5.5.4 Taper Period

Subjects who complete of the Maintenance Period and will not be continuing into the open-label extension study, and subjects who discontinue from the study early, will be tapered off of study medication. Study medication will be administered as equal doses BID in the morning and in the evening approximately 12 hours apart, with food. Each dose should be separated by a minimum of 8 hours and a maximum of 12 hours. A missed dose of study medication may be taken later up to 8 hours before the next scheduled dose; otherwise, the missed dose should not be given. IMP should be administered using the oral dosing syringe provided.

In order to maintain the blind across all dose groups, all subjects who do not continue into the

Confidential Page 46 of 182

open-extension study will participate in a dose-tapering procedure over the course of 8 days. On the first day of the tapering period subjects in the ZX008 0.8 mg/kg/day group will decrease to a dose of ZX008 0.4 mg/kg/day BID (maximum 30 mg/day). After 4 days at this dose level (Study Day 5), subjects randomized to the ZX008 0.8 mg/kg/day group will decrease their dose to 0.2 mg/kg/day. Subjects in the ZX008 0.2 mg/kg/day group will decrease their dose to placebo on the first day of tapering while doses in the placebo group will remain constant throughout the tapering procedure. On Study Day 9, all subjects will stop taking study medication. The taper is expected to take a total of 8 days (Table 4). A new bottle of IMP will ikejilis ele, be started by the subject at each level of the taper step.

Table 4: **Taper Algorithm**

Dandamizad Croun	Taper Step 1 Day 1-4 after study completion or early termination	Taper Step 2 Days 5-8 after study completion or early termination	
Randomized Group ZX008 0.2 mg/kg/day	Placebo	Placebo	
ZX008 0.8 mg/kg/day	ZX008 0.4 mg/kg/day	ZX008 0.2 mg/kg/day	
Placebo	Placebo	Placebo	
Note: maximum daily dose of ZX008 is 30 mg.			

Transition Period 5.5.5

Subjects who complete the Maintenance Period and will be continuing into the open-label extension study will be transitioned from double-blind study medication to open-label ZX008 (Table 5). Study medication will be administered as equal doses BID in the morning and in the evening approximately 12 hours apart, with food. Each dose should be separated by a minimum of 8 hours and a maximum of 12 hours. A missed dose of study medication may be taken later up to 8 hours before the next scheduled dose; otherwise, the missed dose should not be given. Study medication should be administered using the oral dosing syringe provided.

All subjects entering the open-label extension study will be transitioned from their blinded daily dose (placebo, 0.2 mg/kg/day, 0.8 mg/kg/day, or 30 mg/day) to the 0.2 mg/kg dose during the 2-week interval between Visits 12 and 13, without breaking the blind. The IVR/IWR system will assign two bottles of IMP to the subject, one for each step in the transition. A new bottle of IMP will be started by the subject at each level of the transition step. See Section 5.6 for more information about the volume of ZX008 or placebo to be administered.

Table 5: **Transition Algorithm**

Dose Group in Double-Blind Study	Transition Step 1 Day 1-4 after Visit 12	Transition Step 2 Days 5-14 after Visit 12	
ZX008 0.2 mg/kg/day	ZX008 0.2 mg/kg/day	ZX008 0.2 mg/kg/day	
ZX008 0.8 mg/kg/day	ZX008 0.4 mg/kg/day	ZX008 0.2 mg/kg/day	

Confidential Page 47 of 182

Placebo	ZX008 0.2 mg/kg/day	ZX008 0.2 mg/kg/day		
Note: maximum daily dose of ZX008 is 30 mg.				

Subjects who had been randomized to placebo increase their dose to 0.2 mg/kg/day beginning on Day 1 of the transition (the day following Visit 12). Subjects who had been randomized to 0.2 mg/kg/day will continue to receive that dose. Subjects who had been randomized to 0.8 mg/kg/day or were receiving the maximum dose of 30 mg/day decrease to a dose of ZX008 0.4 mg/kg/day, or a maximum of 30 mg/day. After 4 days at this dose level (Day 5), these subjects will decrease their dose to 0.2 mg/kg/day. Subjects will report to the clinic on Day 15 for enrollment into the open-label extension study.

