- Subject does not have a cardiovascular or cardiopulmonary abnormality based on ECHO, ECG or physical examination, including but not limited to trace mitral or aortic valve regurgitation or signs of pulmonary hypertension, and is approved for entry by the central cardiac reader.
- 3. Subject demonstrates a stable baseline with ≥6 convulsive seizures during the 6-week Baseline Period, with a minimum of 2 in the first 3 weeks and 2 in the second 3 weeks
- 4. Subject's parent/caregiver has been compliant with diary completion during the Baseline Period, in the opinion of the investigator (e.g., at least 90% compliant).

Study Product, Dose, and Mode of Administration:

ZX008 is supplied as an oral solution in concentrations of 1.25, 2.5, and 5 mg/mL. Subjects will be randomized to receive 1 of 2 doses of ZX008 (0.2 mg/kg/day, 0.8 mg/kg/day; maximum dose: 30 mg/day) or placebo. Study medication will be administered twice a day (BID) in equally divided doses with food.

Reference Product, Dose, and Mode of Administration:

Matching ZX008 placebo is supplied as an oral solution.

Duration of Treatment:

All subjects will receive ZX008 or matching placebo for up to approximately 16 weeks (Titration Period=2 weeks; Maintenance Period=12 weeks; Taper/Transition Period=2 weeks). After completion of the Maintenance Period, eligible subjects may enroll in the open-label extension study, after completion of the transition. Subjects who do not enroll in the open-label extension study will undergo a taper off of study medication (doses will be administered in a blinded fashion similar to the titration, i.e., doses will be decreased in 4-day increments). Follow-up cardiovascular safety assessments, including ECG and ECHO, will be performed 3 to 6 months following the last dose of study medication.

Criteria for Evaluation:

Efficacy:

- Number of seizures by type
- Convulsive seizure-free interval
- Clinical Global Impression Improvement as assessed by parent/caregiver
- Clinical Global Impression Improvement as assessed by principal investigator
- QOLCE to measure changes in quality of life of the subject
- PedsQL to measure changes in quality of life of the subject
- PedsOL Family Impact module to measure changes in quality of life of the parent/caregiver

Confidential Page 19 of 182

- QoL of parent/caregiver using the EQ-5D-5L scale
- Affective symptoms of parent/caregiver using the HADS scale

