such that treatment outside of the protocol and other than ZX008 is assumed to be in the subject's best interest. Frequent or increased use of rescue medication may be considered indicative of worsening.

- 8. An "actual suicide attempt" as classified by the Columbia-Suicide Severity Rating Scale (C-SSRS).
- 9. It is the investigator's opinion that it is not in the subject's best interest to continue in the study.
- 10. Subject is found to be pregnant while on study.

Discontinuation decisions will be made at each participating site by the site investigator, except that discontinuations due to development of cardiovascular or cardiopulmonary complications are to be made by the IDMSC with input from the IPCAB and the investigator.

If feasible, the process of discontinuation should be discussed with the Medical Monitor. The decisions regarding the discontinuation of the investigational therapy, whether the study medication should be stopped immediately or tapered should be discussed with the Medical Monitor, but final decisions about the process will remain at the discretion of the site principal investigator.

Subjects who are discontinued from the clinical investigation for any reason will not be replaced.

Subjects may withdraw their consent to participate in the study at any time without having to justify the reason for doing so. The decision to withdraw consent and discontinue participation in the study will not prejudice the subject's future medical treatment in any way. Subjects must be discontinued from receiving ZX008 and/or participating in any further study procedures under the following circumstances:

- The subject or the subject's legally authorized representative wishes to discontinue participation in the study.
- The investigator advises that the subject's safety or well-being could be compromised by further participation in the study.
- The sponsor requests that a subject discontinues participation in the study (e.g., due to suspicion of fraud, multiple enrollments in clinical studies, lack of compliance).

The IDSMC may request that the study be terminated after review of the safety information at any time during the study. The IDMSC will review the data for the development of heart valve disease and pulmonary hypertension as they occur on a case-by-case basis and at regular meetings.

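### The taper follows the randomised arm rather than the dose being taken, so a 0.8 mg/kg/day subject tapered after stopping on Study Days 1-4 is stepped up from 0.2 to 0.4 mg/kg/day, and one stopping on Days 5-8 gets no first-step reduction.

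*Protocol*

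**What the plan says.** Section 5.5.4 applies the taper to completers who do not enter the extension, "and subjects who discontinue from the study early, will be tapered off of study medication". Table 4 has one row per randomised group, and its columns cover both completion and early termination. For the high-dose arm, on the first day "subjects in the ZX008 0.8 mg/kg/day group will decrease to a dose of ZX008 0.4 mg/kg/day BID"; taper days 5-8 are at 0.2 mg/kg/day. For the low-dose arm, "Subjects in the ZX008 0.2 mg/kg/day group will decrease their dose to placebo on the first day of tapering". Neither the text nor the table makes the schedule depend on the dose reached. The Synopsis (Duration of Treatment) describes the taper in general terms: "doses will be decreased in 4-day increments".

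Section 5.5.2 and Table 3 set the way up. Everyone starts at "0.2 mg/kg/day (or placebo equivalent) BID". On Study Day 5, "subjects randomized to the ZX008 0.8 mg/kg/day group will increase their dose to 0.4 mg/kg/day", and on Day 9 they reach 0.8 mg/kg/day, with a cap of 30 mg/day throughout.

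Section 4.5 qualifies the taper. On discontinuation, "whether the study medication should be stopped immediately or tapered should be discussed with the Medical Monitor", with the final decision left to the site principal investigator. Section 4.4.2, by contrast, directs a subject withdrawn for pregnancy to complete the taper.

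**The concern.** Table 4 suits a subject already at the target dose, but it is also applied to people who leave during titration. In the high-dose arm, the first taper step of 0.4 mg/kg/day is a reduction only from Day 9 onward. Before that it is either an increase or no change, which contradicts the wording of Section 5.5.4 and of the Synopsis.

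The plan also treats the same exposure in two ways. On Day 4 a low-dose and a high-dose subject are both on 0.2 mg/kg/day. The first goes straight to placebo and the second goes up to 0.4.

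What is at stake is dosing safety in children aged 2 to 18: more drug after a decision to stop, possibly because of an adverse event. Under Section 5.6 the site, the Medical Monitor and the sponsor are all blinded to allocation and concentration. They can read the tables and the study day, but they cannot confirm whether a particular subject's taper would raise the dose.

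**Working it through.** **Inputs.** Doses by study day come from Table 3, taper doses from Table 4, and the 30 mg/day cap from both. All doses are read as total daily doses given in two halves. Any in-clinic dose on Study Day -1 (Section 6.1.3) is ignored.

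**The plan's own figures.** The taper length is 4 + 4 = 8 days, as stated. From the full uncapped dose the steps are 0.8 to 0.4 to 0.2, a true decrease. The schedule works for the subject it was written for.

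**First taper step relative to the current dose, 0.8 arm.** Ratio = step-1 dose / current dose.

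| Last dosing day | Current dose (mg/kg/day) | Step 1 (mg/kg/day) | Ratio | At 25 kg |
|---|---|---|---|---|
| Days 1-4 | 0.2 | 0.4 | 2.0 | 5 to 10 mg/day |
| Days 5-8 | 0.4 | 0.4 | 1.0 | 10 to 10 mg/day |
| Day 9 on | 0.8 | 0.4 | 0.5 | 20 to 10 mg/day |

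The cap does not remove the rise for Day 1-4 leavers. At 75 kg the dose goes from 15 to 30 mg/day (ratio 2.0), and at 90 kg from 18 to 30 mg/day (ratio 30/18 = 1.67).

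**Cumulative dose before and after stopping, 0.8 arm.**

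- Taper total: 4 × 0.4 + 4 × 0.2 = 2.4 mg/kg.
- Stop at end of Day 4: 4 × 0.2 = 0.8 mg/kg before. Taper / before = 2.4 / 0.8 = 3.0. At 20 kg this is 16 mg before and 48 mg after, with the daily dose going from 4 to 8 mg in step 1.
- Stop at end of Day 8: 4 × 0.2 + 4 × 0.4 = 2.4 mg/kg before. Taper / before = 2.4 / 2.4 = 1.0.

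**Comparison with a taper keyed to the last dose step.** From 0.2, go to placebo, as Table 4 already does for the low-dose arm: 0 mg/kg. From 0.4, give 0.2 for four days and then placebo: 4 × 0.2 = 0.8 mg/kg. The excess under the written schedule is 2.4 - 0 = 2.4 mg/kg (Day 4) and 2.4 - 0.8 = 1.6 mg/kg (Day 8).

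**Timing against the titration.** A subject who stops after Day 2 and is tapered would reach 0.4 mg/kg/day on Day 3. Table 3 does not allow that dose until Day 5, and Section 3.5 gives acclimation to the high dose as the reason for titrating.

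**How many subjects.** The protocol gives no early drop-out rate. If 1% to 5% of the 35 subjects in the arm leave on Days 1-8 (an assumption), that is 35 × 0.01 = 0.35 to 35 × 0.05 = 1.75 subjects. The number falls if some are stopped at once, and only the Day 1-4 leavers among them face an increase.

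**The case against.** The strongest reply is that the protocol already offers a way out. Section 4.5 lets the investigator stop drug at once. For Days 1-4 this needs no unblinding: Table 3 has nobody above 0.2 mg/kg/day, and Table 4 itself takes 0.2 straight to placebo. The intent to reduce is clear from the wording, and the randomisation system might be built to prevent a step up. In daily terms the increase is 0.2 to 0.4 mg/kg/day for four days. That is the same increment due on Day 5 anyway, half the arm's target, and within the 0.12 to 0.9 mg/kg/day that Section 1.5 reports for earlier Dravet use. For Days 5-8 the schedule never raises the dose, and how fast to come down from 0.4 is a matter of judgement.

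Much of this stands as a limit on size. The immediate stop makes the problem rarer, the threefold figure compares eight taper days with four dosing days, and the Day 5-8 half is the weaker one. The 1.6 mg/kg excess there depends on the alternative schedule chosen as comparator.

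The defect remains. Section 4.5 supplies no modified taper, so a subject who is tapered still follows Table 4. Tapering is the default in Section 3.1, in Table 1 footnote b and in Section 5.5.4, and it is directed for pregnancy in Section 4.4.2. The protocol describes no system rule that would catch the error, and a system built to Table 4 would reproduce it.

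**Conclusion.** The concern holds. Followed as written, the taper doubles the dose for a 0.8-arm subject who is tapered after stopping on Days 1-4 (1.67-fold at 90 kg because of the cap). It gives no step-1 reduction after stopping on Days 5-8. Both outcomes contradict the protocol's own description of the taper.

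This is a narrow dosing-safety error that should be corrected. It probably concerns no more than one or two subjects, on the assumed 1% to 5% early drop-out and before removing those stopped at once. The dose arithmetic follows directly from Tables 3 and 4 and rests on no outside figure. The document does not show that four days at 0.4 mg/kg/day is hazardous. The objection is that the drug is increased after a decision to stop, at a dose which Day 1-4 leavers have not taken before. Alpha, power and the primary analysis are unaffected.

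**What to change.** Key Table 4, Section 5.5.4 and the IVR/IWR taper kits to the last dose step taken:

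- from 0.8 mg/kg/day: 0.4, then 0.2;
- from 0.4 mg/kg/day: 0.2, then placebo;
- from 0.2 mg/kg/day, in either active arm: placebo, then placebo.

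Add a sentence that no taper step may exceed the current dose. The immediate-stop option in Section 4.5 can stay as it is.

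The cost is a short protocol amendment and a system rule that reads the current dose step as well as the arm. Every tapered subject still takes two four-day bottles, so the blind is kept. A Day 1-4 leaver who is tapered takes eight days of placebo, as a low-dose leaver already does under Table 4. No extra patients or procedures are needed.
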